1.3.5 Pantoprazole

Pantoprazole (Figure 5) is a proton pump inhibitor (PPI) that blocks gastric acid secretion by irreversibly binding to the proton pump.⁹⁴ It is indicated for treatment of GERD with erosive esophagitis and hypersecretion associated with Zollinger-Ellison syndrome. Pantoprazole is commercially available in an intravenous formulation that can be administered as an intermittent bolus or continuous infusion.

[figure not shown]

Figure 5 Structure of pantoprazole.

Pantoprazole and other PPIs are potent OCT2 inhibitors (Figure 6).¹ The IC₅₀ for pantoprazole inhibition of OCT2 is 2.8 mcM and the C_{max} of the drug in children after 0.8 mg/kg (equivalent to 40 mg in adults) was 15 mcM and after a dose of 1.6 mg/kg (equivalent to 80 mg in adults) was 27 mcM,³ which would inhibit OCT2 by >80%.¹

[figure not shown]

Figure 6 Inhibition of OCT2 by pantoprazole.¹

Cimetidine (histamine H₂-receptor antagonist) also inhibits OCT2. In a small study of 9 patients with testicular cancer treated with cisplatin (20 mg/m²/d x 5 days), cimetidine plus verapamil appeared to prevent cisplatin nephrotoxicity (assessed as change in effective renal plasma flow and GFR) compared to a similar historical control population (n=9) treated with cisplatin alone (Figure 7).⁴ Cimetidine does not interfere with the anticancer effect of cisplatin *in vitro* and *in vivo* in an osteosarcoma cell line, indicating that uptake of cisplatin

[figure not shown]

Figure 7 Change in GFR 10 and 21 days after 100 mg/m² cisplatin administered over 5 days without (left) and with cimetidine and verapamil.

into tumor cells is not mediated by OCT2 in osteosarcoma.⁹⁵ Pretreatment of human tumor cells with a proton pump inhibitor enhanced the cytotoxic effect of multiple anti-cancer drugs including cisplatin, and omeprazole pretreatment in mice harboring human tumor xenografts induced sensitivity of the tumors to cisplatin.^{96,97}

The PK and tolerability of single intravenous doses of 0.8 and 1.6 mg/kg of pantoprazole have been studied in children.³ The C_{max} and AUC of IV pantoprazole at 0.8 and 1.6 mg/kg in children aged 2 to 16 years were similar to these PK parameters in adults at 40 and 80 mg (Figure 8). The clearance of pantoprazole in children was 0.2 L/h/kg and the half-life was 1.2 h. Although the t_{1/2} is short, its pharmacodynamic effect is more long lasting.⁹⁴ PPIs interfere with MTX excretion,⁹⁸ but by 20 days after the last cisplatin dose when HDMTX is administered, pantoprazole will be completely cleared.

[figure not shown]

Figure 8 PK of intravenous pantoprazole in children (2-16 yrs) at doses of 0.8 and 1.6 mg/kg compared to adults at 20, 40 and 80 mg.^{3,4}

Pantoprazole is primarily metabolized by CYP2C19, which is genetically polymorphic. CYP2C19 activity is absent in 3% of whites and 20% of Asians, and children with CYP2C19 polymorphisms have slower clearance and longer t_{1/2}.³

The single IV doses of pantoprazole (0.8 and 1.6 mg/kg) were well tolerated. Three adverse events occurred in 18 patients, all of which were mild and judged to be unrelated to pantoprazole.³ The most common toxicities associated with PPIs are diarrhea, nausea, headaches, abdominal pain, fatigue and dizziness.⁹⁴

1.3.6 Serum biomarkers for osteosarcoma

Serum biomarkers for diagnosing osteosarcoma, for monitoring response to treatment, and for detecting disease recurrence would be valuable for the clinical management of the disease and as endpoints for clinical trials. Osteosarcoma is a matrix-producing tumor and radiographic response (tumor shrinkage) to neoadjuvant chemotherapy may not reflect the extent of tumor necrosis, histologically, after neoadjuvant chemotherapy.

Elevated serum alkaline phosphatase (AP) is an independent prognostic factor predicting for poor outcome in osteosarcoma,^{25,99} but serum AP may be derived from other organs and is therefore not specific. Bone-specific AP (BSAP), which is the isoform of AP derived from bone, is a more specific measure of osteoblastic activity.¹⁰⁰⁻¹⁰² BSAP is elevated in patients with OS and is correlated with tumor burden.^{102,103} However, BSAP is also higher in adolescents reflecting periods of bone growth during the adolescent growth spurt. We will investigate the potential role of BSAP as a potential biomarker for OS by measuring serum levels at diagnosis, after neoadjuvant chemotherapy, after surgical resection, and at the end of treatment.

1.3.7 Study Rationale

Current osteosarcoma treatment regimens include drugs that are nephrotoxic and ototoxic, and the damage to kidneys and cochlear hair cells may be irreversible. Preventing these toxicities will improve the outcome in long-term survivors and may also prevent short-term treatment delays and dose reductions that can compromise the efficacy of the treatment regimen and allow for administration of higher cumulative doses of cisplatin. This pilot study evaluates pharmacologically-based approaches to:

- prevent the nephrotoxic effect of HDMTX by prolonging the infusion duration and thereby lowering the risk of drug precipitation in renal tubules, and
- selectively block the uptake of cisplatin into renal tubular cells and cochlear hair cells by inhibiting the organic cation transporter 2 with the proton pump inhibitor, pantoprazole.

A randomized cross-over design, in which patients serve as their own control, will be used to maximize the potential to detect differences in markers of acute kidney injury (NAG, NGAL, KIM-1, cystatin C) and audiograms resulting from altering the infusion duration of HDMTX and from administering pantoprazole with cisplatin.

Two infusion durations of HDMTX will be studied – the standard 4 h duration and more prolonged 12 h infusion duration. Leucovorin rescue will commence 24 h from the start of the infusion. The HDMTX infusions will be divided into 2 blocks (cycles 1 & 2, cycles 3 & 4, see Figure 2), each of which include 4 HDMTX infusions. The order of infusion duration studied in each block will be randomly determined.

[figure not shown]

Figure 9 Amount of cisplatin in the body (blue) and cumulative percent of the dose cleared (orange) for a 60 mg/m² dose infused over 4 h.

[figure not shown]

Figure 10 Plasma concentration-time profile of 1.6 mg/kg pantoprazole infused over 15 min (blue)³ or administered as a 0.3 mg/kg loading dose over 15 min followed by 1.3 mg/kg infused over 4 h (green).

Pantoprazole will either be administered with the first two courses of cisplatin during cycles 1 & 2 or with the third and fourth courses during cycles 3 & 4, and the order will be randomly determined.

Cisplatin is administered as a 60 mg/m² dose infused over 4 h daily x 2 d, and Figure 9 is a PK simulation showing the amount of active drug in the body (assuming a half-life of 20 min) and the percent of the total dose cleared. At steady state, 7.2 mg/m² of active cisplatin is in the body, and by the end of the 4 h infusion, 88% of the total dose has been cleared. Therefore, adequate concentrations to inhibit OCT2 should be present for at least 4 h to prevent cisplatin nephrotoxicity and ototoxicity. Pantoprazole has a short half-life (1.2 h),³ and when administered at a dose of 1.6 mg/kg as a standard 15 min infusion (Figure 10), plasma pantoprazole concentration by the end of the 4 h cisplatin infusion is 1.3 mcM. By administering the same dose as a 0.3 mg/kg loading dose infused over 15 min followed by a 4 h infusion of the remaining 1.3 mg/kg, plasma pantoprazole concentration is 5.9 mcM at 4 h (Figure 10).

The primary endpoint to assess nephrotoxicity will be the AKI biomarkers (cystatin C, KIM-1, NGAL, NAG) described in Section 1.3.3. This will allow us to assess each dose of HDMTX and each course of cisplatin independently. Standard renal function tests (urinalysis, serum creatinine, creatinine clearance, and fractional excretion of magnesium) will also be monitored. Audiograms will be performed after each course of cisplatin to assess ototoxicity. Radiographic response and histological response in the resected tumor specimen after neoadjuvant chemotherapy will be assessed to ensure changes in HDMTX infusion duration and the addition of pantoprazole to cisplatin do not alter the efficacy of chemotherapy. The toxicity of the regimen will be closely monitored, and we will pilot a disease-specific patient reported outcome survey to assess the impact of tumor-related and drug toxicity-related symptoms.

2. STUDY OBJECTIVES

The **primary** objective is to identify more rational, pharmacologically-based drug delivery approaches to prevent nephrotoxicity from HDMTX and cisplatin and ototoxicity from cisplatin in patients with OS by:

- comparing biomarkers of acute kidney injury (KIM-1, NAG, NGAL), glomerular function (cystatin C, creatinine) and plasma and urine MTX concentrations after 12 g/m² of MTX infused over 4 and 12 hours,
- comparing biomarkers of acute kidney injury (KIM-1, NAG, NGAL) and glomerular and tubular function (cystatin C, creatinine, FEMg) after cisplatin administered with and without the OCT2 inhibitor, pantoprazole, and
- comparing hearing loss (audiograms) after cisplatin administered with and without the OCT2 inhibitor, pantoprazole.

Secondary objectives include:

- Comparing the incidence and severity of common toxicities from cisplatin/doxorubicin administered with and without pantoprazole and from HDMTX administered as a 4 and 12 h infusion,
- comparing radiographic response (log ratio of tumor volumes) and histological response (percent tumor necrosis) to two cycles (10 weeks) of neoadjuvant chemotherapy for the two infusion durations of HDMTX and for cisplatin with and without pantoprazole,
- correlating urinary biomarkers of AKI and GFR estimated from serum cystatin C to standard measures of renal function (serum creatinine, urinalysis, estimated creatinine clearance, FEMg),
- building a tissue microarray from biopsy, primary resection and resected metastatic tumors to evaluate the expression of proteins that are responsible for resistance to the drugs in the MAP regimen and to assess expression of proteins that are targeted by new anticancer drugs under development for childhood cancers,
- evaluating serum BSAP as a potential biomarker for OS,
- monitoring nutritional status (weight, arm circumference, skin fold thickness, pre-albumin) in patients receiving the MAP chemotherapy regimen, and
- piloting an osteosarcoma-specific patient reported outcomes survey to assess the incidence and severity of tumor-related and treatment-related symptoms.

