STUDY OBJECTIVES	
Primary objective
 
The primary objective is to identify more rational, pharmacologically-based drug delivery approaches to prevent nephrotoxicity from HDMTX and cisplatin and ototoxicity from cisplatin in patients with OS by:
 
 • comparing biomarkers of acute kidney injury (AKI), glomerular function and plasma and urine MTX concentrations after 12 g/m² of MTX infused over 4 and 12 hours, • comparing biomarkers of AKI, glomerular function and fractional excretion of magnesium (FEMg) after cisplatin administered with and without the OCT2 inhibitor, pantoprazole, and • comparing audiograms after cisplatin administered with and without pantoprazole. 
Secondary objectives
 
 • compare the incidence and severity (grade) of common toxicities from cisplatin/ doxorubicin administered with and without pantoprazole and from HDMTX administered as a 4 and 12 h infusion, • compare radiographic response (log ratio of tumor volumes) and histological response (percent tumor necrosis) to two cycles (10 weeks) of neoadjuvant chemotherapy for the two infusion durations of HDMTX and for cisplatin with and without pantoprazole, • correlate urinary markers of AKI and GFR estimated from serum cystatin C to standard measures of renal function (serum creatinine, urinalysis, estimated creatinine clearance, FEMg), • build a tissue microarray from biopsy, primary resection and resected metastatic tumors to evaluate the expression of proteins that are responsible for resistance

Protocol number: CHP12ST051
 Amendment number:
 Version date: April 2,, 2013

	
to the drugs in the MAP regimen and to assess expression of proteins that are targeted by new anticancer drugs under development for childhood cancers,
 
 • evaluate serum BSAP as a potential biomarker for OS, • monitor nutritional status (weight, arm circumference, skin fold thickness, pre-albumin) in patients receiving the MAP chemotherapy regimen, and • pilot an osteosarcoma-specific patient reported outcomes survey to assess the incidence and severity of tumor-related and treatment-related symptoms.
TEST ARTICLE	Pantoprazole

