- **BSAP** levels will be correlated with tumor volume and presence or absence of metastatic disease at diagnosis. BSAP after 2 cycles of neoadjuvant chemotherapy will be correlated with tumor volume and percent tumor necrosis post-cycle 2. BSAP drawn post-operatively, at the end of therapy and at the time of relapse will be correlated with disease status.
- An osteosarcoma-specific **Patient Reported Outcome survey** will be used to assess disease-related and treatment-related symptoms and tested in the patients enrolled on this trial. The patient reported outcomes will be compared to toxicity data collected from the medical record and to physician assessments of patient status (performance score).

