9. STUDY ADMINISTRATION

9.1 Data collection and management

9.1.1 Confidentiality

Demographic data including each patient's name, MRN, DOB, and a unique patient study number is entered and stored in Oncore CRM (Forte Research), the CCCR's clinical trial management system. Data regarding markers of Acute Kidney Injury (Cystatin-C, KIM-1, NGAL, NAG) will be collected using secure OnCore electronic case report forms (eCRFs). Results of standard renal function tests, audiograms, bone-specific alkaline phosphatase assays, nutritional assessments, and response assessments (radiographic and histologic) as well as toxicity data will also be entered into Oncore eCRFs. Patient related outcomes forms

Protocol number: CHP12ST051
Amendment number:
Version date: April 2, 2013

completed by a parent will be stored in a locked file cabinet in the CTRB. These forms will have patient identifiers (name, DOB, MRN).

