APPENDIX 3 PATIENT REPORTED OUTCOME SURVEY
OSTEOSARCOMA PATIENT SURVEY

PATIENT ID _____

DATE _____

Since the last time I filled this form out . . .	Never (0 times)	Rarely (less than once a week)	Sometimes (1 to 3 times a week)	Often (almost daily)	Almost Always (daily)
I feel too tired to get out of bed					
I feel like I'm going to throw up					
I throw-up or vomit					
My stomach hurts					
I do not feel as hungry as I use to					
Foods taste different or funny					
I have diarrhea					
I have constipation					
I have a ringing sound in my ears					
I have trouble hearing some things					
My mouth or throat hurts					
I am in pain					
I have trouble keeping up with school work because of being in the hospital or feeling too sick					
I have trouble falling asleep					
I wake up at night because of pain					
I don't see my friends as much anymore because I am too busy with doctors and hospital visits					
I don't do as many fun things anymore because I feel tired or sick					
I don't have fun doing things I used to like to do					
I feel nervous, worried, or anxious					
I have trouble doing daily activities like eating, drinking, putting on clothes					
I have answered these questions before (circle one)	YES	NO	I Don't Know		
Compared to the last time I answered these questions, I feel (circle one)	BETTER	WORSE	THE SAME	I DON'T KNOW	
I would like to meet with someone at the hospital talk about how I feel (circle one)	YES	NO	I DON'T KNOW	I AM ALREADY MEETING WITH SOMEONE

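### The patient survey is meant to assess incidence and severity of symptoms, but all 20 rated statements record frequency only, so graded severity cannot be obtained from it

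*Combined protocol and SAP*

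**What the plan says.** - **Objective.** Section 2 sets as a secondary objective "piloting an osteosarcoma-specific patient reported outcomes survey to assess the incidence and severity of tumor-related and treatment-related symptoms". The synopsis repeats it: "pilot an osteosarcoma-specific patient reported outcomes survey to assess the incidence and severity of tumor-related and treatment-related symptoms".
- **Instrument.** Appendix 3 gives one set of response options for every rated statement. They run from no occurrences, through "Rarely (less than once a week", "Sometimes (1 to 3 times a week" and "Often (almost daily", up to daily. The stem reads "Since the last time I filled this form out".
- **Timing.** The Schedule of Study Procedures places the survey at baseline, day 1 of cycles 2 to 6, pre-op and end of therapy.
- **Analysis.** Section 6.1.2 states: "The patient reported outcomes will be compared to toxicity data collected from the medical record". The same sentence adds a comparison with the physician's performance score. No scoring method is given.
- **Respondent.** Section 9.1.1, on data storage, refers to survey forms "completed by a parent will be stored in a locked file cabinet". The form itself is written in the first person and shows fields for patient ID and date only.

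**The concern.** Frequency and severity are different quantities. Take one patient with mild pain every day and another with severe pain up to three times a week. The first marks the top category and the second marks the middle one. Nothing on the form records that the second patient's pain was worse. This follows from the response options alone and assumes no scoring rule.

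The stake is a stated secondary objective of which one half has no data behind it, even with perfect completion. There is also a consequence for the Section 6.1.2 comparison. Sections 6.1.2 and 8.3 collect toxicities from grade 2 upwards, so if those records are the comparator, they are already filtered by severity while the survey counts any occurrence. A mismatch between the two could then reflect the filter, and would say little about how well the survey performs, which is what a pilot of the instrument is meant to show.

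**Working it through.** No power, error rate or event count is involved, and the plan states no figure to reproduce. The check is a count of Appendix 3, set beside the objective.

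**Step 1: what the form asks.**
- Rated statements: 20.
- Function or social impact: 5 (keeping up with school, seeing friends, doing fewer fun things, losing enjoyment of usual things, managing daily activities).
- Symptoms: 20 − 5 = 15 (fatigue, nausea, vomiting, stomach pain, appetite, taste, diarrhoea, constipation, ringing in the ears, hearing, mouth or throat pain, general pain, falling asleep, waking from pain, anxiety). The split is a judgement at the margin, hence about 15 and about 5.
- Statements answered on the frequency scale: 20 of 20. Statements with a severity or intensity scale: 0 of 20.
- Remaining questions: 3, on having completed the form before, feeling better or worse overall since the last form, and wishing to talk to someone. None rates a symptom.

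**Step 2: what each part of the objective needs.**
- Incidence needs a record of whether the symptom occurred. Any answer above the lowest category supplies that.
- Severity needs a grade or intensity. It would have to come from a response scale (none exists) or from a derivation rule (Section 6.1.2 gives none).
- Some wording carries an implicit threshold: tiredness that keeps the patient in bed, pain that wakes the patient, feeling sick as against vomiting. These items still record only how often that state occurred.

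**Step 3: two separate features of the form.**
- *Recall window.* There are 1 + 5 + 1 + 1 = 8 scheduled forms (baseline, cycles 2 to 6, pre-op, end of therapy). At the first there is no earlier form for the stem to refer to, and no other window is given. The other 7 windows follow from Section 3.3.1 (cycles of 5 and 4 weeks, recovery of 1–2 weeks) and surgery at week 11. They run from about 1–2 weeks (pre-op to cycle 3, taking pre-op as just before surgery) to about 4–6 weeks. The first of them is longer if the baseline form is completed early in the screening period of up to 2 weeks.
- *Respondent.* Section 9.1.1 mentions parent completion, and eligibility is under 30 years with no lower age limit stated, so parent completion is plausible for some patients. The appended form has nowhere to record it.

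Neither feature bears on whether severity is measured. Step 2 settles that alone.

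**The case against.** The best defence has several parts.

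- **The mismatch is one word.** Elsewhere the aim is put more loosely: the patient's view of symptoms (synopsis), their impact (Section 1.3.7), or assessing and testing symptom items (Section 6.1.2). That is true, but both formal statements of the objective name severity.
- **The items carry some severity information.** They do, coarsely, as Step 2 grants. They do not give a grade.
- **Clinicians grade severity under CTCAE anyway.** They do, but that is a different source and does not meet an objective set for a patient survey.
- **It is only a pilot.** A pilot can test wording and feasibility. It cannot produce an answer to a question that was never asked.

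The defence succeeds against some stronger readings that a reader might infer:

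- *That the plan intends agreement with CTCAE grade.* Section 6.1.2 does not name grade for this comparison, and Section 5.4 also tracks ungraded measures, so a comparison on occurrence remains open.
- *That the baseline answer cannot be interpreted.* The options are mostly weekly rates, so a first-time respondent can still give a usable answer. One question also identifies a first completion, and Section 6.1.2 plans no change-from-baseline analysis of the survey.
- *That patient and parent answers are pooled.* The only basis is a sentence about storage, and nothing says how such forms would be analysed. Section 9.1.1 also says the forms carry name, date of birth and record number, which the appended page does not show, so that page may not be the full form in use.

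**Conclusion.** The point holds in a limited form. All 20 rated statements record frequency, none grades severity, and no derivation is planned. The survey can therefore deliver occurrence and frequency, but not the graded severity that the objective names. It would be wrong to attribute this to the missing baseline window or the missing respondent field; those are minor, separate defects of the same form.

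The conclusion assumes that the response options in Appendix 3 are those in use and that no scoring guide exists outside the documents. The respondent point also assumes that the header shown is complete, which is less certain. Only a secondary pilot objective is affected. The primary endpoints, the randomised comparisons of nephrotoxicity and ototoxicity, the sample size and the interim review do not depend on the survey. The change is still worth making, because severity that is not asked at the time cannot be recovered later from these forms.

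**What to change.** Choose one of two routes for the main point:

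1. Add a short severity rating, for example none, mild, moderate or severe, to the symptom items in Appendix 3. The cost is a slightly longer form, with about 15 extra responses per completion.
2. Keep the form, restate the objective in the synopsis and Section 2 as incidence and frequency, and limit the Section 6.1.2 comparison with medical-record toxicity to occurrence, stating the grade from which a toxicity counts as recorded. The cost is a few sentences of text and the loss of the severity aim.

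Under either route, make two small corrections to the form: give the first (baseline) form its own fixed recall window, and add a box for patient or parent as respondent. These cost one line each.
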